10. STATISTICAL CONSIDERATIONS AND ANALYTICAL PLAN

10.1 Study Endpoint Assessment

10.1.1 Primary Endpoint

Since our primary thesis is that GLASSIA will increase islet engraftment in the early perioperative period our primary endpoint for which the study is powered is a mechanistic assessment of the functional islet mass early (day 75) post transplant. We will rely on the frequently sampled intravenous glucose tolerance test (FSIGT) from which an AUC for insulin secretion correlates with islet mass for our primary mechanistic assessment of functional islet mass. Data from the CIT06 trial, which performed this test on all patients at day 75, will serve as the control. Such controls increase the power of the trial making it likely that we will be able to detect differences between treated and control groups should GLASSIA exert the hypothesized benefit to engraftment.

10.1.2 Secondary Endpoints

Secondary objectives of this study will assess whether AAT treatment compared to control therapy at the time of islet transplantation, improves the rate of insulin independence over time (1 and 2 years post op), metabolic control and reduces the risk of cardiovascular and renal complications from diabetes.

By examining multiple secondary endpoints it is likely that some variables will be found significantly different between the two treatment groups, but these findings may be Type 1 errors. Appropriate qualifiers will be reported with any significant secondary findings. Secondary endpoints are grouped into two groups: key secondary endpoint and other secondary endpoints. The key secondary endpoint is separated from the other secondary endpoints because it provides direct evidence of the durability of the primary outcome at one year after the final infusion. By identifying the other important secondary endpoints in the protocol we expect favorable changes in these endpoints will provide stronger evidence for a causal relationship than would result from observed significant differences in a large group of secondary endpoints. However, because there are still a large number of other secondary endpoints, if we adjust for the many multiple comparisons then there will be little chance of observing a statistically significant difference. Therefore, we will not adjust for multiplicity comparisons even for the other secondary endpoints.

Most of the secondary endpoints are measured before transplant, at day 75 (A1c, MMT, FSIGT, MAGE, c-peptide and Beta score) and at one year post-initial transplant (HbA1c, fasting and 90 minute MMTT, c-peptide, glucose, and c-peptide glucose creatinine ratio, MAGE, HYPO, Clarke survey, and Beta score). We will compare these markers with those in the CIT-06 controls using student's t-test, nonparametric test (e.g., Mann-Whitney U test, Wilcoxon signed rank test), or chi-square test when appropriate. A pre-post analysis will be used for these variables. For continuous variables that are normally distributed or that can be transformed to a normal distribution, we will compute an appropriate estimate and 95% confidence interval for the mean change and a paired t-test for testing that the mean change is zero. If an appropriate normalizing transform cannot be identified then a signed-rank test will be used to test for a significant change. Similarly, a McNemar test will be used to test for a significant change for dichotomous outcome variables.

For those continuous secondary endpoints that are only observable after transplantation or for whom

change from baseline are not meaningful we will compute estimates of the mean and 95% confidence intervals. Similarly, for binary endpoints we will compute the observed rates and exact 95% confidence intervals. Levels of these markers will be compared with those in the CIT-06 controls using student's t-test or nonparametric test (e.g., Mann-Whitney U test) when appropriate.

Regression models for continuous longitudinal data (mixed models) will be used to describe the profiles of change over time for each of the response variables where measurements are repeated over time. Similar models will be used to model dichotomous variables over time.

Survival analysis models will be used to compare time to becoming insulin dependent and to identify risk factors through Kaplan-Meier estimates and Cox regression models.

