10.1.3 Exploratory Endpoints

Exploring novel approaches to monitoring islet graft injury will serve as the basis for hypotheses generation in future trials. We will calculate descriptive statistics for the safety and efficacy of the new approaches. Adverse events rates will be tabulated and 95% confidence intervals (CI) will be calculated. We will calculate the mean, median, minimum, maximum, inter-quartile ranges, and 95% CI of loss of engrafted islets estimated by early post infusion release of insulin specific DNA, TAT and C3a. Success rate and 95% CI will be estimated.

Other secondary and exploratory endpoints include relative functional engrafted islet mass, the proportion achieving insulin independence, the proportion achieving HbA1c \leq 6.5% and an absence of severe hypoglycemic events, the proportion achieving HbA1c $<$ 7.0%, reduction in HbA1c of at least 1 point, the change in Clarke score, c-peptide, Glycemic lability index (LI), glucose and glucose variability. These endpoints will also be analyzed using descriptive statistics.

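### About 70 unadjusted secondary comparisons with a non-randomised cohort are credited with stronger causal evidence, which the plan's own concession about the length of the list undercuts

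*Combined protocol and SAP*

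**What the plan says.** Section 4.1.2 gives a key secondary endpoint, insulin independence at four time points. A long list of other secondary endpoints follows, mostly compared with CIT-06 at several times and counted from both the first and the last infusion.

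For the analysis, Section 10.1.2 says: "We will compare these markers with those in the CIT-06 controls using student's t-test, nonparametric test" or a chi-square test. It gives no significance level and no sidedness. On multiplicity, the same section makes four statements in turn:

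- A warning: "it is likely that some variables will be found significantly different between the two treatment groups, but these findings may be Type 1 errors".
- A promise: "Appropriate qualifiers will be reported with any significant secondary findings".
- A claim about the endpoints named in the protocol: "we expect favorable changes in these endpoints will provide stronger evidence for a causal relationship than would result from observed significant differences". The comparator that completes this sentence is a large group of secondary endpoints.
- A concession, "because there are still a large number of other secondary endpoints", followed by the decision "Therefore, we will not adjust for multiplicity comparisons even for the other secondary endpoints". The reason given is that adjustment would leave little prospect of a significant result.

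Section 10.1.3 then names several of the same endpoints (islet mass, insulin independence, the HbA1c measures, Clarke score, c-peptide, lability index, glucose variability) and says: "These endpoints will also be analyzed using descriptive statistics".

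**The concern.** The third and fourth statements do not fit together. Naming endpoints in advance strengthens the evidence when the list is short. The plan claims that benefit by contrast with a large group, and in the next sentence says that its own group is large. The promised qualifiers are undefined, and they do not withdraw the claim.

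The comparison is also with an earlier cohort in an open-label, non-randomised study (Section 7.8.1), so even a fully adjusted test would not support a causal reading by itself.

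What is at stake is how the results are used. If the primary endpoint is missed, a few nominally significant secondary results could be presented, with the protocol's backing, as evidence that AAT works. An analyst also cannot tell from 10.1.2 and 10.1.3 whether these endpoints are mainly to be tested or described, or at what level.

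**Working it through.** **The plan's own figures.** The documents state no family-wise error rate for the secondary endpoints. The only figures given for them are the half widths in Table 9, which reproduce as 1.96 × SD / √20: SD 0.7 gives 0.31, 55 gives 24, 750 gives 329, 4 gives 1.8 and 200 gives 88. They imply 95% intervals and n = 20, which is the basis for assuming two-sided 5% per test below.

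**Count of comparisons with CIT-06 in Section 4.1.2.** Four means 1 and 2 years × first and last infusion.

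| Endpoint | Comparisons |
|---|---|
| Percent change in insulin (3 times × first/last) | 6 |
| FSIGT islet mass | 3 |
| Three HbA1c/hypoglycaemia composites × 2 periods | 6 |
| Severe hypoglycaemic events | 4 |
| HbA1c | 4 |
| Clarke score | 2 |
| β-score | 4 |
| CGMS (2 measures × 4) | 8 |
| MMTT (4 measures × 4) | 16 |
| MAGE, LI, HYPO, CPGCR (4 each) | 16 |
| **Total** | **69** |

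The insulin-independence items repeated from the key secondary add 4 (73). The second- and third-transplant proportions add 8 (77). Both together give 81. Marker correlations, centre rates, and cardiovascular and renal endpoints are left out. First and last infusion coincide for anyone with one infusion; keeping first-infusion times only reduces the 81 to 46. One comparison per measure gives about 20.

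**Formula.** Take m test statistics that are standard normal under no effect, with common correlation ρ, and c = 1.96. Then

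P(at least one, favouring AAT) = 1 − ∫ [Φ((c − √ρ·u)/√(1−ρ))]^m φ(u) du.

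For either direction, subtract Φ((−c − √ρ·u)/√(1−ρ)) inside the bracket. At ρ = 0 these reduce to 1 − 0.975^m and 1 − 0.95^m; for m = 70 that is 1 − 0.975^70 = 0.830 and 1 − 0.95^70 = 0.972. The documents give no correlation, so 0.5 is assumed and 0 to 0.8 is shown.

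| m | Direction | ρ = 0 | ρ = 0.3 | ρ = 0.5 | ρ = 0.8 |
|---|---|---|---|---|---|
| 70 | either | 97.2% | 88.3% | 69.9% | 32.8% |
| 70 | favouring AAT | 83.0% | 51.0% | 35.7% | 16.4% |
| 46 | either | 90.6% | 78.4% | 60.3% | 29.2% |
| 46 | favouring AAT | 68.8% | 43.0% | 30.5% | 14.6% |
| 20 | either | 64.2% | 54.0% | 41.9% | 22.4% |
| 20 | favouring AAT | 39.7% | 28.0% | 21.0% | 11.2% |

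With 70 tests, the either-direction chance falls below 50% at ρ of about 0.66. The chance favouring AAT falls below 50% at about 0.31.

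**Check with a less uniform structure.** A simulation with 73 tests in 20 blocks, correlation 0.8 within a block and 0.3 between blocks, gave 80.5% in either direction and 44.9% favouring AAT. With 0.5 between blocks it gave 65.4% and 33.4%; with 0.1 between blocks, 88.4% and 58.8%.

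**Key secondary endpoint.** Section 10.1.2 describes it as durability at one year after the final infusion. Section 4.1.2 lists four time points under that heading and repeats all four among the other secondary endpoints.

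**The case against.** The best defence is that this is a 20-patient Phase 2 study that calls itself a pilot. Openly unadjusted secondary endpoints with a written warning about Type 1 errors are a defensible choice in that setting. The sponsor's worry about power is also real. Bonferroni over 70 tests sets each at 0.05/70 = 0.00071, and the difference detectable with 80% power (20 versus 24 subjects) rises from 0.85 SD to 1.28 SD. Both points stand, and for that reason the remedy below does not ask for adjustment.

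The causal sentence is also comparative and claims no proof. That stands too. But its comparator is a large group of endpoints, and the plan places its own list in that class.

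Several stronger readings are tempting and go beyond the documents:

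- *Every comparison is tested at a full 5%.* No level or sidedness is stated; 5% two-sided is an assumption here. The markers that 10.1.2 names for comparison are tied to day 75 and one year, and repeated measures also go to mixed models, so 70 is an upper reading of the test plan. The results for 46 and 20 tests are shown for that reason.
- *The plan refuses any ordering.* It separates a key secondary endpoint from the rest and says why; what it lacks is a formal gate.
- *Section 10.1.3 makes these endpoints descriptive only.* Its wording is that they are also analysed descriptively, which can sit beside the tests. The two sections are unclear together rather than flatly opposed.

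**Conclusion.** The concern holds as a fault in the stated inference. The claim of stronger causal evidence is not supported for about 70 unadjusted, overlapping comparisons with a non-randomised cohort, and the promised qualifiers do not repair it.

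At correlation 0.5 the chance of at least one false significant result favouring AAT is 36% for 70 tests (16% to 83% over correlations 0.8 to 0), 31% for 46 (15% to 69%) and 21% for 20 (11% to 40%). Even the mildest case, 11%, is over four times the nominal 2.5%.

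A reader might infer that a false AAT benefit is more likely than not. That is true of a false result in either direction (70% for 70 tests at 0.5), which includes results against AAT. In the favourable direction it needs a correlation below about 0.31, or one-sided 5% tests (51.6% for 70 tests at 0.5), which the plan does not specify. Nor does the expected count settle it: 70 × 0.025 = 1.75 false favourable results on average, but correlated results cluster, so the average can exceed one while the chance of any stays below one half.

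All figures assume no true effect on any endpoint, two-sided 5% per test and the correlations shown. They cover chance only; bias from the historical cohort would come on top. The primary test is not affected.

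**What to change.** 1. In Section 10.1.2, delete the sentence claiming stronger causal evidence.
2. Label all other secondary endpoints exploratory. Report estimates with 95% confidence intervals and nominal p-values, state the alpha and sidedness, and say that none of them supports an efficacy claim. Align 10.1.2 with 10.1.3 so that each endpoint has one stated analysis.
3. Name one key secondary time point; 10.1.2 already describes one year after the final infusion. Remove its duplicate from the other secondary list in 4.1.2. Allow a confirmatory claim on it only if the primary test (day-75 insulin independence, Sections 4.1.1 and 10.3.1) succeeds, at the same one-sided 2.5%.

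The cost is protocol and SAP wording. No patients or data are needed, and none of the power that the sponsor fears losing through adjustment is given up. The small downside is that a nominally significant secondary result can no longer stand alone as evidence of effect.

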4.1 Study Endpoints

Since our primary thesis is that GLASSIA will increase islet engraftment in the early perioperative period our primary endpoint for which the study is powered is a comparison of insulin independence rates of GLASSIA treated versus control patients at day 75 post transplant. We are fortunate to have permission to utilize data from the CIT-06 trial which will allow a large number of control patients. Since our proposed trial was directly derived from CIT-06 in terms of entry criteria, treatment regimen and post transplant monitoring except for treatment with GLASSIA and related mechanistic studies, these cohorts provide us a highly relevant comparator and allow us to enroll more GLASSIA treated patients than if a randomized trial. This increases the power of the trial making it likely that we will be able to detect differences between treated and control groups should GLASSIA exert the hypothesized benefit to engraftment.

For our primary mechanistic assessment to measure engrafted functional islet mass we will rely on the frequently sampled intravenous glucose tolerance test (FSIGT) from which an AUC for insulin secretion correlates with islet mass. Each of the 24 CIT-06 patients had this test performed at day 75. Of note, we had previously considered use of a glucose potentiated arginine stimulation test for this purpose. However, no CIT-06 patients had this test performed¹³¹⁻¹³².

Because the assessment of islet graft function is dependent on complex physiologic relationships between the graft and its recipient, no single test adequately addresses the metabolic impact of the transplant. Therefore, HbA1c and the number of episodes of severe hypoglycemia will be used as clinically relevant measures of islet graft function for secondary endpoints, and additional stimulatory tests of islet graft function utilizing MMTT, glucose, and the CPGCR will be used to assess secondary endpoints. Also, the effect of islet graft function on glycemic control (HbA1c), glycemic lability (MAGE and LI), hypoglycemia (Clarke and HYPO scores), glucose variability (CGMS®), cardiovascular impact, and renal impact will be assessed as additional secondary endpoints¹³²⁻¹³⁶. Each of these were collected in CIT-06 patients and will add to the robustness of our comparison of the metabolic outcome between GLASSIA treated and control CIT-06 subjects.

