7.8 Study Treatment Assignment Procedures

7.8.1 Blinding and Randomization

This is an open-label, non-randomized study. Therefore, no blinded treatment codes are required for the assignment of study treatment.

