We have chosen to transplant 20 subjects. This will provide approximately 87% power to detect a difference of 50% insulin independence rate in islet transplanted subjects versus the estimated 16.7% insulin independence rate. Table 8 displays minimal detectable differences with 70%, 80% and 90% power. The smallest difference that can be detected with 90% power by a one-sided 2.5% level binomial test is 52% compared to 16.7%. The minimal detectable difference is 47% compared to 16.7% with 80% power. Using a one-sided test with 10% type 1 error rate, we could detect a medium effect of slightly more than 2 fold difference (38% vs. 16.7%) with 70% power.

Table 8 Minimum Detectable Difference for Insulin Independence Rate

Power	Minimum detectable difference
70%	43% vs. 16.7%
80%	47% vs. 16.7%

90%	52% vs. 16.7%
-----	---------------

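### Secondary markers are compared with the non-randomised CIT-06 cohort without baseline adjustment, and tested for pre-post change that cannot isolate AAT; use a baseline-adjusted cohort comparison where a usable baseline exists in both cohorts

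*Combined protocol and SAP*

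**What the plan says.** Section 10.1.2 gives two inferential routes for markers measured before transplant and again at day 75 or one year.

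- Between cohorts: "We will compare these markers with those in the CIT-06 controls using student's t-test", a nonparametric test or a chi-square test, as appropriate. The nonparametric examples are Mann-Whitney and Wilcoxon signed-rank. No covariate is named.
- Within subjects: "A pre-post analysis will be used for these variables", with "a paired t-test for testing that the mean change is zero", a signed-rank test if no transformation achieves normality, and McNemar for binary outcomes.

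The section also plans models: "Regression models for continuous longitudinal data (mixed models) will be used to describe the profiles of change over time". It gives these no cohort term, baseline term or contrast. Kaplan-Meier and Cox methods are planned for time to insulin dependence.

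On design, section 7.8.1 states: "This is an open-label, non-randomized study". Section 10.3.1 states: "We have chosen to transplant 20 subjects". Section 1.1 gives 24 CIT-06 patients as controls. Section 4.1 says the trial derives from CIT-06 apart from GLASSIA and related mechanistic work, and concludes that "these cohorts provide us a highly relevant comparator". Section 2.2 sets the secondary aim as AAT treatment against control therapy.

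**The concern.** The within-subject tests do not address the secondary aim. Every subject in both cohorts receives islets, induction and close glycaemic management, so HbA1c, Clarke score and insulin dose should improve from baseline even if AAT does nothing. A significant paired test says that the transplant package works.

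The between-cohort tests do address the aim, but without randomisation nothing balances the cohorts at baseline, and a difference there feeds into the estimate. The direction depends on what is compared. Section 4.1.2 defines insulin requirement and Clarke score as change from baseline; for the other markers with a baseline, 10.1.2 does not say whether level or change enters the test. Level and change respond to the same imbalance with opposite signs.

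The signed-rank test needs pairs, and 20 GLASSIA subjects and 24 CIT-06 subjects are not paired.

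The stakes rise because 10.1.2 expects favourable changes in the secondary endpoints to strengthen a causal reading and declines to adjust for multiplicity.

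**Working it through.** **Inputs from the documents.** n = 20 GLASSIA (10.3.1) and 24 CIT-06 (1.1); HbA1c SD 0.7 (Table 9, section 10.3.2).

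**Inputs assumed.** The documents give neither the baseline-to-follow-up correlation (rho) nor the baseline difference between cohorts (d, in SD units). I take rho from 0 to 0.7 and d from 0 to 1.

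**Step 1: the plan's own precision.** Table 9 is 1.96 × SD/√20. For HbA1c, 1.96 × 0.7/√20 = 0.307 (stated 0.31). The other five rows also reproduce: 0.307, 24.1, 328.7, 1.75 and 87.7 against 0.31, 24, 329, 1.8 and 88. These are one-sample figures. For the cohort difference the half-width is t(42) × SD × √(1/20 + 1/24) = 2.018 × 0.7 × 0.3028 = 0.428, about 1.4 times the Table 9 figure.

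**Step 2: bias with no true effect.** With equal SDs, the expected bias is rho × d for levels, (rho − 1) × d for change, and 0 for ANCOVA. At d = 0.5 and rho = 0.5 these are +0.25, −0.25 and 0 SD. Simulation with 6,000 trials per case, 20 against 24 and d = 0.5, gives:

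| rho | Bias in SD: level / change / ANCOVA | False positives: level / change / ANCOVA |
|---|---|---|
| 0.3 | +0.16 / −0.34 / 0.01 | 7.9% / 15.7% / 4.8% |
| 0.5 | +0.25 / −0.25 / 0.00 | 12.8% / 13.0% / 4.8% |
| 0.7 | +0.35 / −0.15 / 0.00 | 21.2% / 9.5% / 5.0% |

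At the Table 9 SD for HbA1c, 0.25 SD is 0.25 × 0.7 = 0.175 percentage points. Table 9 does not say whether its SDs are pre- or post-transplant, so that conversion is only indicative.

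**Step 3: effect on interval width.** The ratio of adjusted to unadjusted half-width is [t(41)/t(42)] × √((1 − rho²) × VIF), with VIF = 1 + d² × (20 × 24/44)/42. At d = 0.5, VIF = 1 + 0.25 × 10.909/42 = 1.065.

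| rho | d = 0.5 | d = 1.0 |
|---|---|---|
| 0 | 1.033 | 1.123 |
| 0.2 | 1.012 | 1.100 |
| 0.3 | 0.985 | 1.071 |
| 0.5 | 0.894 | 0.973 |
| 0.7 | 0.737 | 0.802 |

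Adjustment narrows the interval only if rho exceeds about 0.16, 0.25, 0.38 or 0.46 for d = 0.3, 0.5, 0.8 or 1.0. With chance imbalance only, an uninformative covariate widens it by about 1.3%, and three by about 4%.

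**Step 4: what adjustment cannot reach.** Add an unmeasured cohort effect of 0.5 SD (d = 0.5, rho = 0.3). ANCOVA is then biased by 0.49 SD with 36% false positives; the level test is worse (0.64 SD, 54%), and the change test looks better (0.14 SD, 7%) only because two biases happen to cancel. With no baseline difference and rho = 0.5, the same unmeasured effect produces 37% false positives for the level test and 45% for ANCOVA, because the ANCOVA interval is narrower around the same bias.

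**Step 5: which markers qualify.** Inclusion criterion 5 (section 3.1) holds stimulated c-peptide below 0.3 ng/mL at entry, so its baseline is at a floor. Appendix 1, note 27, makes baseline FSIGT optional. HbA1c and Clarke score are scheduled at screening and on the wait list, and section 4.1 says both were collected in CIT-06. The change-from-baseline endpoints for Clarke score and insulin requirement presuppose a baseline in both cohorts.

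**The case against.** The plan can be defended on several counts. Section 10.1.2 does not attribute pre-post change to AAT; the comparison with CIT-06 is a separate sentence. The section warns of Type 1 errors and promises qualifiers, and 10.1.3 assigns several of these endpoints to descriptive statistics. The signed-rank entry could be a slip, since the later CIT-06 comparison in 10.1.2 names only Mann-Whitney. Models are also planned, so raw tests are not the whole analysis. All of that is fair, but none of it supplies a baseline-adjusted cohort estimate: the mixed models only describe profiles, and the qualifiers concern multiplicity, not imbalance.

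A reader might infer that adjustment would remove the bias of a non-randomised comparison. It would not: it deals only with the measured, correctly modelled baseline value, as step 4 shows. A reader might also infer that it tightens intervals at no cost. That depends on a correlation the documents do not give, and with low correlation or large imbalance the interval widens.

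First-infusion IEq/kg may look like a natural second covariate. Section 7.4 has GLASSIA infused after release testing confirms the islets, so AAT cannot alter the dose. But section 4.1 does not list IEq/kg among the CIT-06 data, and it does not fit endpoints timed from the last infusion.

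**Conclusion.** The point holds as a worthwhile, inexpensive improvement for a defined set of continuous markers. The pre-post tests cannot answer the AAT question, and the cohort tests leave measured baseline differences in the estimate, with a sign that depends on an unstated choice between level and change. Under the assumed 0.5 SD imbalance and correlation of 0.5, that is about ±0.25 SD of bias and about 13% false positives, against about 0 and 5% for ANCOVA. These sizes rest on assumed values; the actual imbalance between the cohorts may be smaller or larger.

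The documents do not support extending this to every secondary marker: stimulated c-peptide has a floor baseline, FSIGT an optional one, and 10.1.2 itself sets apart endpoints observable only after transplant. Nor do they support treating the adjusted result as free of confounding.

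**What to change.** In section 10.1.2:

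1. For continuous markers with a usable pre-transplant value in both cohorts (e.g. HbA1c, Clarke score, insulin requirement), make the between-cohort estimate an ANCOVA of the follow-up value on cohort and baseline, or give the planned mixed model those terms and a stated cohort contrast. Report the adjusted difference with its 95% CI.
2. Name the qualifying markers in advance, exclude stimulated c-peptide and FSIGT, and state how missing baselines are handled.
3. Label the paired t, signed-rank and McNemar results descriptive.
4. Delete the signed-rank test from the list of tests against CIT-06.
5. Add first-infusion IEq/kg only as a sensitivity covariate, only for endpoints timed from the first infusion, and only if CIT-06 can supply it.
6. State that differences in era, site and selection remain unadjusted.

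The cost is mainly wording, plus confirmation that comparable CIT-06 baseline values can be obtained. Statistically, it is about 1% wider intervals if baseline proves uninformative, and up to about 12% in the worst case tabulated (rho = 0, d = 1).
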